### 2.3 5-FU/Capecitabine

5-FU is an antineoplastic antimetabolite that blocks the methylation reaction of deoxyuridylic acid to thymidylic acid, and in consequence, interferes with the synthesis of DNA and to a lesser extent RNA. Given the essential nature of DNA and RNA for cell growth, the generation of a thymine deficiency can result in cell death, most pronounced on rapidly growing cells, as found commonly in a variety of cancers.

In the US, 5-FU is given as a continuous infusion IV where it is partially excreted by the kidneys (20%) and the remainder is metabolized by the liver. Half-life is approximately 20 minutes and it can cross the blood-brain barrier. 5-FU is formally FDA approved in colorectal cancer, breast, stomach, and pancreatic cancers, but is widely used off label in a variety of cancers including mucosal squamous head and neck cancers and cutaneous squamous cell carcinomas.

Adverse events associated with 5-FU include: stomatitis, nausea, diarrhea, neutropenia, neurotoxicity, hand-foot syndrome, as well as risk of a hypersensitivity reaction in patients with a dipyrimidine dehydrogenase deficiency. 5-FU is teratogenic in lab animals and rated pregnancy class D.

Capecitabine, an oral pre-drug of 5-FU, was first approved for use in the United States by the FDA in 1988. It is presently approved for use in patients with metastatic breast cancer, both as monotherapy and in combination with docetaxel. It is also approved for both metastatic

colorectal cancer and as an adjuvant following resection of Dukes' Stage C colon cancer. Despite this rather limited FDA labeling, it is widely used both as a single agent and in combination for a multiplicity of other tumors including gastric, pancreatic, and squamous cell cancers of the head and neck.

While the standard FDA approved dose as listed in the package insert is 1250 mg per meter squared twice daily for two weeks followed by seven-day rest period, most clinicians have found this dose to be intolerable on a chronic basis. Therefore, it has become conventional to initiate dosing at 1000 mg per meter squared twice daily instead. The drug is presently available as Xeloda in two pill sizes, 150 mg and 500 mg. When the patent expires on Xeloda in 2013 is unclear when or if generic equivalents will become available and in what doses the pills will be manufactured. Should a generic version become available while this trial is open and accruing patients, the protocol will be modified accordingly.

The mechanism of action of capecitabine is conversion to 5-fluorouracil *in vivo*, occurring mostly in the liver. Cells subsequently metabolize 5-fluorouracil to FdUMP and FUTP. FdUMP inhibits thymidylate synthase, thereby decreasing pools of thymidine triphosphate available for DNA synthesis. FUTP can substitute for UTP during RNA synthesis, thereby disrupting protein synthesis from the abnormal RNA. Capecitabine is absorbed rapidly and conversion into 5-FU is rapid with peak levels reached within two hours post ingestion. Concomitant food consumption with capecitabine lowers both peak concentration and area under the curve concentration of capecitabine substantially. The elimination half-life of capecitabine and its metabolites is quite fast, on the order of approximately one hour. However, the cellular consequences of thymidylate synthase and RNA synthesis disruption are much more prolonged as they are dependent on regeneration of normal pools of the enzymes and RNA precursors.

Metabolism and bioactivation of capecitabine is hepatic, while excretion of capecitabine and its metabolites is predominantly accomplished by the kidneys with minimal fecal excretion. Therefore, dose adjustments for both renal insufficiency and hepatic insufficiency are warranted. In the case of mild renal impairment with a creatinine clearance greater than 50 mL/min, no dose adjustment is recommended. With moderate renal impairment (creatinine clearance 30-49 mL/min), a 20% dose reduction is recommended. While there is no defined dose adjustment for patients with hepatic dysfunction, caution should be used in administering capecitabine to patients with markedly abnormal hepatic function. Additional details on warnings and dose modifications for hepatic and renal dysfunction are available in the capecitabine package insert.

Common adverse events associated with capecitabine include diarrhea (stomatitis from gastrointestinal toxicity), coagulopathy, cardiotoxicity, fetal harm, hand-foot syndrome, hyperbilirubinemia, and bone marrow suppression, resulting in anemia, thrombocytopenia, and neutropenia.

There are known drug-drug interactions between 5-FU/capecitabine and coumadin anticoagulants, as well as 5-FU/capecitabine and phenytoin. While co-administration of these agents is not prohibited, frequent monitoring of prothrombin time and phenytoin levels in patients on concurrent 5-FU/capecitabine is warranted.

### 2.3 Rationale

There are no drugs presently approved by the US Food and Drug Administration for treatment of metastatic squamous cell carcinoma of the skin. However, several drugs are used off-label, based on a limited number of investigations in the medical literature. Prior case reports or case

studies have reported objective responses using cisplatin in combination with bleomycin, methotrexate, or doxorubicin. Phase II data using retinoic acid and interferon-alpha alone or in combination with cisplatin demonstrated response rates of 34% and 43%, respectively.

A Phase I trial attempted to combine cis-retinoic acid, IFN alpha-2a, cisplatin, and 5-FU/Leucovorin; however, cytopenic toxicities limited the full administration of this regimen. A more recent adjuvant Phase III trial in post-surgical patients with CSCC used cis-retinoic acid and interferon alpha versus observation, but failed to reduce the risk of recurrence.

Capecitabine has also been used against CSCC with modest response rates, but the data is reported as two case series. In virtually every disease studied in which 5- fluorouracil is clinically active, capecitabine has demonstrated similar activity. Previously, we have treated a number of skin squamous cell carcinoma patients with capecitabine off-label and have noted dramatic and prolonged antitumor effects in a number of these patients. Additionally, we found that with the ease of titrating the oral doses of capecitabine, we could reduce drug toxicity, and patients were able to tolerate therapy for an extended period of time. Furthermore, the use of an oral agent may be favored by patients rather than an IV infusion.

Unfortunately, the studies discussed above suffer from small patient numbers, combined squamous and basal cell cohorts, and the demonstration of chemotherapy-induced toxicity. While no standard therapy exists for CSCC, we propose that a cytotoxic drug with documented response rates in CSCC combined with an immunomodulatory agent, also known to have benefit in this patient group, may result in overall improved response rates.

Therefore, we intend to conduct a phase II, single arm trial of interferon alpha-2b and 5-FU/capecitabine in patients with advanced or recurrent squamous cell carcinoma of the skin for which local regional treatment would not be expected to be curative. Because there is no known first line standard of care treatment for these patients and because of the known activity of 5-fluorouracil analogues and interferon-alpha in this disease, our intention is to allow patients to be treated in the first line with the combination of interferon alpha-2b and 5-FU/capecitabine without regard to prior chemotherapy, other than prior systemic treatment with 5-fluorouracil analogues.

It is our intention to use commercially available PEG interferon alpha-2b and 5-FU/capecitabine for this trial. Based on prior experience, a high percentage of these patients are able to attain these drugs for off-label use in this situation. However, we have found in some cases, insurance companies have been reticent to approve coverage for capecitabine. We believe that by generating data showing that capecitabine in combination with interferon alpha-2b is safe and effective in this group of patients, its use will become more widely accepted based on this proposed clinical trial as well as to provide continued support of the benefit of immunotherapy in this disease. For patients that are not approved for oral capecitabine, we will use continuous infusion 5-FU as described above.

### **3. PATIENT SELECTION**

#### **3.1 Inclusion Criteria**

- 3.1.1 Patients must have histologically or cytologically confirmed squamous cell carcinoma of the skin. Patients who present with "squamous cell carcinoma of unknown primary lesions" at the time of diagnosis will be eligible if patients have a plausible primary skin site removed in the past. Similarly, patients with neck, parotid, or facial lymph nodes positive for squamous cell carcinoma with no identifiable mucosal primary would also be eligible.

- 3.1.2 Patients must have measurable disease, defined by RECIST v1.1 as at least one lesion that can be accurately measured in at least one dimension of  $\geq 10$  mm by CT, MRI, or calipers. See section 9.2 for the evaluation of measurable disease.
- 3.1.3 There is no limitation to prior treatments with local, regional, topical or systemic agents, except for prior systemic treatment with 5-fluorouracil or prodrugs thereof. Prior topical treatment with 5-fluorouracil is permitted. Patients who are on chronic daily doses of prednisone of greater than 10 mg are excluded. There is no restriction on timing of last treatments as long as patients have recovered from all expected toxicities and at least 21 days have passed since last administration.
- 3.1.4 Age  $\geq 18$  years. Because no dosing or adverse event data are currently available on the use of 5-FU/Capecitabine or IFN alpha-2b in patients  $<18$  years of age, children are excluded from this study.
- 3.1.5 Life expectancy of greater than 3 months.
- 3.1.6 ECOG performance status  $\leq 2$  (Karnofsky  $\geq 60\%$ ; see Appendix A).
- 3.1.7 Patients must have normal organ and marrow function as defined below:
 

Absolute neutrophil count	$\geq 1,500/\text{mcL}$
Platelets	$\geq 75,000/\text{mcL}$
Total Bilirubin	$< \text{ULN}$ or up to 2x ULN if patient has clinically documented Gilbert's syndrome (elevated unconjugated bilirubin from decreased UGT1A1 activity)
AST(SGOT)/ALT(SGPT)	$\leq 2.5x$ institutional upper limit of normal or up to 5x ULN if known to be caused by liver metastasis
Creatinine Clearance	$\geq 50 \text{ mL/min}$ by either Cockcroft-Gault formula or 24 hr urine collection analysis.
- 3.1.8 Patients must not be candidates for curative locoregional treatments. Patients with recurrent locoregional disease following surgery and/or radiation for who a resection is unacceptably morbid and unlikely to be curative are eligible. Patients must be reviewed at the Moffitt Cutaneous Tumor Board prior to enrolling on trial to verify unresectability.
- 3.1.9 The effects of 5-FU/Capecitabine and IFN alpha-2b on the developing

human fetus at the recommended therapeutic dose are unknown. For this reason and because anti-metabolites are known to be teratogenic, women of child-bearing potential and men must agree to use adequate contraception (barrier method of birth control; abstinence) prior to study entry and for the duration of study participation. Should a woman become pregnant or suspect she is pregnant while participating in this study, she should inform her treating physician immediately.

3.1.10 Ability to understand and the willingness to sign a written informed consent document.

### 3.2 Exclusion Criteria

3.2.1 Patients who have had chemotherapy or radiotherapy within 21 days (6 weeks for nitrosoureas or mitomycin C) prior to entering the study or those who have not recovered from adverse events due to agents administered more than 3 weeks earlier.

3.2.2 Patients may not be receiving any other investigational agents.

3.2.3 Patients with known brain metastases should be excluded from this clinical trial because of their poor prognosis and because they often develop progressive neurologic dysfunction that would confound the evaluation of neurologic and other adverse events.

3.2.4 History of allergic reactions attributed to compounds of similar chemical or biologic composition to either 5-FU/Capecitabine or Interferon.

3.2.5 Uncontrolled, ongoing illness including, but not limited to, ongoing or active infection, symptomatic congestive heart failure, unstable angina pectoris, myocardial infarction <30 days, CVA/TIA <30 days, cardiac arrhythmia, or psychiatric illness/social situations that would limit compliance with study requirements.

3.2.6 Pregnant women are excluded from this study because 5-FU/Capecitabine is an anti-metabolite agent with the potential for teratogenic or abortifacient effects. Because there is an unknown but potential risk for adverse events in nursing infants secondary to treatment of the mother with 5-FU/Capecitabine, breastfeeding should be discontinued if the mother is treated with 5-FU/Capecitabine. Pregnancy testing will be completed on all female participants of child-bearing potential by urine analysis.

3.2.8 Any heart or lung transplant patient on immunosuppressive agents. Renal transplant patients are allowed if patient is willing to reduce immunosuppressive agents and understand risk of rejection and possible need to return to dialysis. Patients with CLL or other hematologic malignancies are allowed as long as they meet other criteria listed above.

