### **4.1 Capecitabine Administration**

Drug administration will be on an outpatient basis. Capecitabine will be administered at an initial dose of 800 mg/m^2 by mouth twice daily on days 1-14 of a 21 day cycle with days 15-21 off. This cycle will be repeated every 21 days during the study for a maximum of 9 cycles as tolerated. Administration via feeding tube in patients unable to swallow is permitted. For severe side effects, dose reductions are listed in Table 5. Reported adverse events and potential risks are described in Section 6.

Capecitabine tablets should be swallowed with water within 30 min after a meal. The calculated dose by body surface area (BSA) will be rounded down to allow as close to as total daily dose of 1600 mg/m^2 divided as closely as possible into AM and PM doses of 800 mg/m^2 using a combination of 150 mg and 500 mg tablets. There will be no modification of BSA calculation based on idealized body weight or other corrective factor.

**4.1.1 Storage:** Capecitabine tablets should be kept a room temperature

**4.1.2 Pill Diary:** The patient will be requested to maintain a medication diary for review at the end of each cycle of treatment and reconciled with a pill count.

If the patient is clinically stable after 3 cycles, then a diary review and pill counts may be discontinued.

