**6.1 Expected potential toxicities of 5-FU/Capecitabine:**

Hematologic: anemia, neutropenia, thrombocytopenia

Constitutional: fatigue, pyrexia, edema, pain, chest pain

Dermatologic: hand-foot syndrome, dermatitis, skin discoloration, alopecia, nail disorders

Gastrointestinal: diarrhea, nausea, vomiting, stomatitis, abdominal pain, gastrointestinal motility disorder, constipation, oral discomfort, upper GI inflammatory disorders, gastrointestinal hemorrhage, ileus

Hepatic: hyperbilirubinemia

Infections: bacterial or viral

Metabolic: appetite decreased, dehydration

Musculoskeletal: back pain, arthralgia

Neurologic: peripheral sensory neuropathy, headache, dizziness, insomnia, taste disturbance

Ocular: eye irritation, vision abnormal

Psychiatric: mood alteration, depression

Pulmonary: dyspnea, cough, pharyngeal disorder, epistaxis, sore throat

Vascular: venous thrombosis

Cardiac: myocardial infarction/ischemia, angina, dysrhythmias, cardiac arrest, cardiac failure, sudden death, electrocardiographic changes, and cardiomyopathy.

Dihydropyrimidine Dehydrogenase Deficiency: Rarely, unexpected, severe toxicity (eg, stomatitis, diarrhea, neutropenia and neurotoxicity) associated with 5-fluorouracil has been attributed to a deficiency of dihydropyrimidine dehydrogenase (DPD) activity.

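### The visible eligibility criteria do not expressly exclude a patient already known to have DPD deficiency, which the protocol names as a cause of severe 5-FU toxicity

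*Combined protocol and SAP*

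**What the plan says.** The hazard is named twice. Section 2.3 (5-FU/Capecitabine) lists, among the adverse events of 5-FU, "risk of a hypersensitivity reaction in patients with a dipyrimidine dehydrogenase deficiency". Section 6.1, whose heading covers both 5-FU and capecitabine, says that rare, severe 5-FU toxicity "has been attributed to a deficiency of dihydropyrimidine dehydrogenase (DPD) activity". Section 2.3 also explains that capecitabine works by conversion to 5-FU in the body, so both treatment routes are concerned.

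On eligibility, 3.2.4 excludes a "History of allergic reactions attributed to compounds of similar chemical or biologic composition to either 5-FU/Capecitabine or Interferon". Criterion 3.1.3 allows any prior treatment "except for prior systemic treatment with 5-fluorouracil or prodrugs thereof"; prior topical 5-FU is allowed.

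On dosing, section 4.1 states "Capecitabine will be administered at an initial dose of 800" mg/m² twice daily, on days 1-14 of a 21-day cycle. Section 4.2 starts infusional 5-FU at 800 mg/m² on days 1-4. Neither section adjusts the start for DPD deficiency. The reductions in section 5.1 follow a grade 3 or 4 toxicity or a low blood count.

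**The concern.** The protocol identifies a patient characteristic that can turn the study drug into a serious hazard, but does not carry it into the entry criteria. The wording in 2.3 may hide the gap. Because the DPD effect is called a hypersensitivity reaction there, a reader could assume that the allergy criterion covers it. That criterion looks back to a reaction that has happened, and a patient who is known to be deficient but has never been exposed has none.

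What is at stake is avoidable harm to a patient whose risk is already on record. The trial's inference is not at stake.

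**Working it through.** This is mainly a check of the text, followed by a short bound on size.

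**1. Criteria that can be read.** 3.1.1 to 3.1.10 give 10, 3.2.1 to 3.2.6 give 6, and 3.2.8 gives 1: 10 + 6 + 1 = 17. None of the 17 names DPD deficiency. The numbering passes from 3.2.6 to 3.2.8, so the result holds for the visible text only.

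**2. Could another provision cover the case indirectly?**
- 3.2.4 needs a past allergic reaction. It might catch someone who had reacted, for example to topical 5-FU, but not a known carrier without a reaction.
- 3.2.5 concerns uncontrolled, ongoing illness. An enzyme deficiency without symptoms does not plainly fit.
- 3.1.7 sets limits for neutrophils, platelets, bilirubin, transaminases and creatinine clearance. None of these measures DPD activity.
- 3.1.3 removes anyone whose deficiency came to light through systemic 5-FU or a prodrug. This narrows the gap but leaves patients whose deficiency is known by another route.
- Section 2.3 refers to the label: "Additional details on warnings and dose modifications for hepatic and renal dysfunction are available in the capecitabine package insert". On its most natural reading this concerns hepatic and renal dysfunction.
- The investigator-judgment clause in 4.4 is a reason to stop treatment, so it acts after dosing has begun.
- The study calendar (section 8) has no DPD test. It does have a pre-study medical history.

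**3. Protection after the start.** Interferon is given weekly at the infusion center (4.3), so symptoms may be noticed early. Scheduled blood counts, chemistry and physical examinations fall at weeks 1, 4 and 7. A 14-day capecitabine course or a 4-day infusion can therefore finish before the next scheduled neutrophil count.

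**4. Size.** The inputs are n = 30 (total enrolment, 11.2 and 11.3) and p, the share of otherwise eligible candidates with known deficiency. The documents do not give p. I assume 0 to 0.1%. The expected number is n × p, and the chance of at least one is 1 − (1 − p)^n.

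| p (assumed) | Expected of 30 | Chance of at least one |
|---|---|---|
| 0 | 0 | 0 |
| 0.01% | 0.003 | 0.30% |
| 0.1% | 0.03 | 2.96% |

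For that chance to reach 5%, p would have to be 1 − 0.95^(1/30) = 0.00171, or about 0.17%.

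**5. Starting dose in context, capecitabine only.** Section 2.3 gives a labelled dose of 1250 and a conventional dose of 1000 mg/m² twice daily. The study dose is 800/1250 = 64% and 800/1000 = 80% of these. The comparison does not apply to infusional 5-FU, and a lower dose for everyone is not an adjustment for DPD deficiency.

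**The case against.** The strongest reply has four parts.

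- **Absence is not proved.** Item 3.2.7 cannot be seen. This stands, and the point is conditional on it.
- **The hazard and the remedy only partly match.** Section 6.1 describes toxicity that is rare and unforeseen, which points to unrecognised deficiency. A criterion on known deficiency would not reach those patients, and the documents describe no route by which a patient without prior systemic 5-FU would have been diagnosed. This stands too, and it is why the expected number is close to zero.
- **Eligibility permits enrolment but does not compel it.** The investigator takes a history and has the protocol's own two warnings, and would probably decline. This also stands. What remains is that the written criteria do not require it.
- **The frequency range is assumed.** The 3.0% upper figure simply reflects the chosen ceiling of 0.1%. That is correct.

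A reader might infer more than the documents support. One tempting reading is that the protocol should require DPD testing, or that it exposes an appreciable number of patients. The documents give no frequency of deficiency, known or unknown, so neither claim can be built on them. Another is that the Gilbert's syndrome clause in 3.1.7 is a precedent for excluding a documented enzyme condition. It is not: that clause relaxes a bilirubin limit so that such patients can enter. The better parallel is 3.2.3, which excludes a condition when it is known: "Patients with known brain metastases should be excluded from this clinical trial".

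**Conclusion.** The point holds in a narrow form and is minor. A patient with known DPD deficiency, no prior systemic 5-FU and no past allergic reaction is not expressly excluded by the visible criteria, and would start at the standard dose by either route. The most likely number of such patients in the trial is 0 of 30, with a chance of at least one of 0 to 3.0% under the assumed frequency.

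The conclusion rests on three things: 3.2.7 does not already contain the exclusion, the patient meets all other criteria, and the label reference in 2.3 is not meant to bring in every label warning as an entry rule. The text does not show that such a patient would in practice be treated. The Simon two-stage rules, the response endpoint and the survival analyses are unaffected.

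**What to change.** First check 3.2.7 in the full protocol. If it does not address the matter, add a separate item to 3.2, apart from the allergy criterion: *Known dihydropyrimidine dehydrogenase (DPD) deficiency*. Base it on the medical history already scheduled at the pre-study visit.

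The cost is one line of text in an amendment. It needs no new procedure, the loss of accrual is negligible, and the sample size and decision rules stay as they are.

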### 3.3 Inclusion of Women and Minorities

Both men and women and members of all races and ethnic groups are eligible for this trial.

